### **7.3.4 Caffeine**

Subjects will refrain from consuming caffeinated beverages starting 24 hours before and until after the last PK blood sample has been collected and for 24 hours before the screening visit and follow-up visit. At all other times, caffeinated beverages or xanthine-containing products will be limited to amounts of no more than 6 units per day (1 unit = 120 mg of caffeine).

### **7.3.5 Smoking**

Smoking is not permitted during the trial.

## **7.4 Diet, Fluid, and Activity**

### **7.4.1 Diet and Fluid**

Subjects will fast (no food or drink except water) for at least 2 hours before study drug dosing.

Water is permitted until 1 hour before TAK-954 administration. Water may be consumed without restrictions beginning 1 hour after TAK-954 dosing.

Lunch, dinner, and snacks will be provided on Day 1. Breakfast, lunch, dinner, and morning and afternoon snacks will be provided on all other domiciled days.

### **7.4.2 Activity**

Subjects will avoid unaccustomed strenuous physical activity (eg, weight lifting, running, bicycling) from the screening visit until administration of the study drug, throughout the trial, until the follow-up visit.

## **7.5 Criteria for Discontinuation or Withdrawal of a Subject**

The primary reason for discontinuation or withdrawal of the subject from the study or study drug should be recorded in the electronic case report form (eCRF) using the following categories.

1. Treatment discontinuation due to an AE: The subject has experienced an AE that requires early termination because continued participation poses an unacceptable risk to the subject's health or the subject is unwilling to continue in the study because of the AE.
2. Significant protocol deviation: The discovery that the subject did not meet protocol entry criteria or did not adhere to protocol requirements, and continued participation poses an unacceptable risk to the subject's health.
3. Lost to follow-up: The subject did not return to the clinic, and attempts to contact the subject were unsuccessful. Attempts to contact the subject must be documented in the subject's source documents.
4. Voluntary withdrawal: The subject wishes to withdraw from the study. The reason for withdrawal, if provided, should be recorded in the eCRF.
5. Note: All attempts should be made to determine the underlying reason for the withdrawal and, where possible, the primary underlying reason should be recorded (eg, withdrawal due to an AE should not be recorded in the voluntary withdrawal category).
6. Study termination: The sponsor, IRB, IEC, or regulatory agency terminates the study.
7. Other.

Note: The specific reasons should be recorded in the “specify” field of the eCRF.

## **7.6 Procedures for Discontinuation or Withdrawal of a Subject**

The investigator may discontinue a subject's trial participation at any time during the trial when the subject meets the trial termination criteria described in Section [7.5](#). In addition, a subject may discontinue participation without giving a reason at any time during the trial. Should a subject's participation be discontinued, the primary criterion for termination must be recorded by the investigator. In addition, efforts should be made to perform all procedures scheduled for the early termination visit.

## **7.7 Subject Replacement**

If a subject discontinues from the trial, a replacement subject may be enrolled, if deemed appropriate by the investigator and sponsor.

## **8.0 CLINICAL STUDY MATERIAL MANAGEMENT**

### **8.1 Clinical Study Drug**

Details regarding the composition and extemporaneous preparation of the active drug are found in the pharmacy manual. Clinical study drug will be packaged to support enrollment and replacement subjects as required. When a replacement subject is required, the sponsor must be contacted before dosing.

#### **8.1.1 Clinical Study Drug Labeling**

Clinical study drug will be affixed with a clinical label in accordance with regulatory requirements.

#### **8.1.2 Clinical Study Drug Inventory and Storage**

Clinical study drug must be stored in a secure, limited-access location under the storage conditions specified on the label. Inventory (receipt and dispensing) of study drug must be recorded by an authorized, unblinded person at the trial site.

#### **8.1.3 Clinical Study Drug Blinding**

This is an open-label trial.

#### **8.1.4 Clinical Trial Blind Maintenance/Unblinding Procedure**

This is an open-label trial.

#### **8.1.5 Accountability and Destruction of sponsor-Supplied Drugs**

The investigator is responsible for keeping accurate records of the clinical study drug received from the sponsor or designee and the amount remaining at the conclusion of the trial. For all trial sites, the local country sponsor personnel or designee will provide appropriate documentation that must be completed for clinical study drug accountability, return, and destruction.

## **9.0 STUDY PROCEDURES**

The following sections describe the trial procedures to be performed and data to be collected as indicated in the schedule of study procedures (Section 3.0). For each procedure, subjects are to be assessed by the same investigator or site personnel whenever possible. Please note that it may become necessary to perform the following procedures at unscheduled time periods, at the investigator's discretion.

### **9.1 Administrative Procedures**

#### **9.1.1 Informed Consent Procedure**

Informed consent must be obtained before the subject enters the trial and before any protocol-directed procedures are performed. The requirements of informed consent are described in [Appendix B](#).

##### *9.1.1.1 Assignment of Screening and Subject Numbers*

All consented subjects will be given a unique screening number that will be used to identify the subject for all procedures that occur before enrollment. Each subject will be assigned only 1 screening number. Screening numbers must not be reused for different subjects. Any subject who is screened multiple times will be assigned a new screening number for each screening event.

All eligible subjects will receive a subject number. The subject number identifies the subject for all procedures occurring after enrollment. Once a subject number is assigned to a subject, it can never be reassigned to another subject. A single subject cannot be assigned more than 1 subject number.

##### *9.1.1.2 Study Drug Assignment*

On Day 1, subjects will be assigned a subject number in ascending numerical order at the clinical site. The subject number determines the order in which the subjects will receive TAK-954.

#### **9.1.2 Inclusion and Exclusion**

Each subject will be assessed according to the eligibility criteria provided in Section 7.0.

#### **9.1.3 Medical History/Demography**

Qualified site personnel will collect subject significant medical history (past and concurrent medical conditions), per the site's standard of care and appropriate clinical judgment, and subject demographics.

#### **9.1.4 Concomitant Medications**

Qualified site personnel will review each subject's prior and concomitant medication use. Medications are defined as prescription and over-the-counter drugs, vaccines, supplements, nutraceuticals, and oral herbal preparations.

## **9.2 Clinical Procedures and Assessments**

### **9.2.1 Full Physical Exam**

Qualified site personnel will conduct full physical examinations.

A neurological assessment will be part of the physical examination and mainly will consist of tests of sensory and motor functions (eg, reflexes, coordination, and gait).

### **9.2.2 Height and Weight**

Body weight and height will be obtained with the subject's shoes off and jacket or coat removed.

### **9.2.3 BMI**

BMI equals a subject's weight in kilograms divided by height in meters squared ( $BMI = \text{kg}/\text{m}^2$ ). BMI will be rounded to the nearest whole number according to the standard convention of 0.1 to 0.4, round down, and 0.5 to 0.9, round up.

### **9.2.4 Vital Signs**

Body temperature will be measured with an oral (temperature taken at floor of the mouth) or tympanic thermometer. The same method (ie, oral or tympanic) must be used for all subsequent measurements for each subject and should be the same for all subjects.

Subjects should rest in a semirecumbent position for at least 5 minutes before vital signs are measured. Vital signs will include heart rate, respiratory rate, and systolic and diastolic blood pressure. The same method (eg, same size cuff, manual or automated) must be used for all measurements for each subject and should be the same for all subjects.

Subjects should continue to rest in a semirecumbent position from the time of dosing until 4 hours postdose, except to stand for the measurement of standing vital signs (if needed) or other trial-related procedures.

### **9.2.5 12-Lead ECG**

Special care must be taken for proper lead placement by qualified personnel. Skin should be clean and dry before lead placement. Subjects may need to be shaved to ensure proper lead placement.

Subjects should be resting in a semirecumbent position for at least 5 minutes before each ECG measurement.

QT intervals with Fridericia correction method (QTcF intervals) will be calculated in this trial.

An ECG will be obtained at screening. This measurement will be used as the baseline assessment. The principal investigator should arrange to have a trial cardiologist available as needed to review ECG tracings with abnormalities.

During the treatment period, if a subject demonstrates an increase in QTcF interval  $\geq 40$  milliseconds compared with a predose baseline measurement, the ECG will be repeated

within 5 minutes. The average value of the QTcF interval from the 2 ECGs will represent the value at that time point. If the average QTcF interval increase from baseline for any postdose time point is  $\geq 40$  milliseconds, the subject will continue to be monitored by repeat 12-lead ECGs every 60 minutes for at least 4 hours or until the QTcF interval is within 40 milliseconds of the baseline value. If prolongation of the QTcF interval  $\geq 40$  milliseconds persists, a consultation with a trial cardiologist may be appropriate, and the sponsor should be notified.

If the QTcF interval is  $\geq 500$  milliseconds, the sponsor should be notified, and the ECGs should be reviewed by a cardiologist. The subject should be monitored by telemetry (until the QTcF interval is  $< 500$  milliseconds) or should be considered for transfer to a location where closer monitoring is available.

If the subject has unstable hemodynamics or any clinically significant dysrhythmias noted by telemetry, the subject should be immediately transferred to an acute care setting for definitive therapy.

If repeat ECGs are required, the clinical site will decide whether to leave the electrodes in place or mark the position of the electrodes for subsequent ECGs. To mark the position of the electrodes, 12-lead electrode sites will be marked on the skin of each subject with an ECG skin marker to ensure reproducible electrode placement.

The following ECG parameters will be recorded: heart rate, PR interval, QRS interval, QT interval, QTcF interval, and the interpretation of the ECG profile by the principal investigator.

### **9.2.6 Study Drug Administration**

On Day 1 of the treatment period, study drug (a single dose of TAK-954) will be administered as described in Section 6.1.

### **9.2.7 AE Monitoring**

AE monitoring begins after signing of the ICF. Changes in subject health status from the baseline assessment until study drug administration should be captured in the subject's medical history. A complete description of AE collection and procedures is provided in Section 10.0.

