## **10.0 ADVERSE EVENTS**

### **10.1 Definitions and Elements of AEs**

An AE is defined as any untoward medical occurrence in a clinical investigation subject who has signed informed consent to participate in a study; it does not necessarily have to have a causal relationship with the treatment.

An AE can therefore be any unfavorable and unintended sign (eg, a clinically significant abnormal laboratory finding), symptom, or disease temporally associated with the use of a drug, whether or not it is considered related to the drug.

An untoward finding generally may:

- Indicate a new diagnosis or unexpected worsening of a preexisting condition. (Intermittent events for preexisting conditions or underlying disease should not be considered AEs.)
- Necessitate therapeutic intervention.
- Require an invasive diagnostic procedure.
- Require discontinuation or a change in dose of study medication or a concomitant medication.
- Be considered unfavorable by the investigator for any reason.

Diagnoses versus signs and symptoms:

- Each event should be recorded to represent a single diagnosis. Accompanying signs (including abnormal laboratory values or ECG findings) and symptoms should NOT be recorded as additional AEs. If a diagnosis is unknown, signs and symptoms should be recorded appropriately as an AEs.

Laboratory values and ECG findings:

- Changes in laboratory values and ECG parameters maybe considered AEs if they are judged to be clinically significant (ie, if some action or intervention is required or if the investigator judges the change to be beyond the range of normal physiologic fluctuation). Laboratory retests and continued monitoring of an abnormal value are not considered interventions. In addition, repeated or additional noninvasive testing for verification, evaluation, or monitoring of an abnormality is not considered an intervention.
- If abnormal laboratory values or ECG findings are the result of pathology for which there is an overall diagnosis (eg, increased creatinine in renal failure), only the diagnosis should be reported appropriately as an AE.

Preexisting conditions:

- A preexisting condition (present at the time of signing of informed consent) is considered a concurrent medical history condition and should NOT be recorded as an AE. A baseline evaluation (eg, laboratory test, ECG, x-ray) should NOT be recorded as an AE unless related to a study procedure. However, if the subject experiences a worsening or complication of such a

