concurrent medical history condition, the worsening or complication should be recorded appropriately as an AE (worsening or complication occurs after informed consent is signed). Investigators should ensure that the event term recorded captures the change in the condition (eg, worsening of...).

- If a subject has a preexisting episodic condition (eg, asthma, epilepsy), any occurrence of an episode should be captured as an AE only if the episodes become more frequent, serious, or severe in nature, and investigators should ensure that the AE term recorded captures the change from baseline in the condition (eg worsening of...).
- If a subject has a degenerative concurrent condition (eg, cataracts, rheumatoid arthritis), worsening of the condition should be captured as an AE only if occurring to a greater extent than would be expected. Again, investigators should ensure that the AE term recorded captures the change in the condition (eg, worsening of...).

Worsening of AEs:

- If the subject experiences a worsening or complication of an AE after the first administration of study medication or after any change in study medication, the worsening or complication should be recorded as a new AE. Investigators should ensure that the AE term recorded captures the change in the condition (eg, worsening of...).

Changes in severity of AEs:

- If the subject experiences a change in the severity of an AE that is not associated with a change in study medication, the event should be captured once, with the maximum severity recorded.

Preplanned surgeries and procedures:

- Preplanned procedures (surgeries or therapies) that were scheduled before signing of informed consent are not considered AEs. However, if a preplanned procedure is performed early (eg, as an emergency) because of worsening of the preexisting condition, the worsening of the condition should be captured appropriately as an AE. Complications resulting from any planned surgery should be reported as AEs.

Elective surgeries and procedures:

- Elective procedures performed where there is no change in the subject's medical condition should not be recorded as AEs but should be documented in the subject's source documents. Complications resulting from an elective surgery should be reported as AEs.

Overdose:

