## **10.2.8 Collection and Reporting of AEs, SAEs, and Abnormal LFTs**

### *10.2.8.1 Collection Period*

Collection of AEs (AEs, SAEs, and abnormal LFTs) will commence when the subject signs the informed consent. Routine collection of AEs will continue until the follow-up visit on day 15 ( $\pm 2$  days). For subjects who discontinue before the administration of study medication, AEs will be followed until the subject discontinues study participation.

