7.5 Medical History and Concurrent Medical Conditions

Medical history is defined as significant conditions or diseases that resolved at or prior to the time of informed consent. Concurrent medical conditions are defined as significant conditions or diseases that are present or ongoing at signing of informed consent.

Medical history and concurrent medical conditions will be coded by system organ class and preferred term using the Medical Dictionary for Regulatory Activities (MedDRA, version 21.0 or higher). No summary statistics for medical history and concurrent medical conditions will be provided.

Medical history and concurrent medical conditions will be listed by subject number. The listing will contain subject identifier, system organ class (SOC), preferred term (PT), whether there was any medical history or concurrent condition, and, if yes, a detail of the medical history or concurrent condition.

There will be no inferential analysis of medical history and concurrent medical conditions.

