7.11.1 Adverse Events

An adverse event (AE) is defined as any untoward medical occurrence in a clinical investigation subject who has signed informed consent to participate in a study; it does not necessarily have to have a causal relationship with study participation. A treatment-emergent adverse event (TEAE) is defined as any sign, symptom, syndrome, or new illness, regardless of relationship to study drug, which occurs on or after the administration of the study drug and no more than 30 days after receiving the study drug (onset date minus date of last dose $+1 \leq 30$). A TEAE may also be a pretreatment AE or a concurrent medical condition diagnosed prior to the date of study drug that increases in severity after the start of dosing. Any event with partially or completely missing onset date information will be considered treatment emergent unless the available information indicates that the onset occurred outside the window (onset date - date of last dose $+1 > 30$) or onset date prior to the first dose.

All AEs will be coded by system organ class (SOC) and preferred term (PT) using the Medical Dictionary for Regulatory Activities (MedDRA, version 21.0 or higher).

AEs are recorded in the eCRF as being related or not related to study drug and study procedure. AEs that are recorded as related to study drug and/or study procedure will be summarized separately. AEs will also be presented by intensity/severity (mild, moderate, and severe).

When calculating the frequency and percentage of subjects who reported AEs, a subject will be counted only once for each SOC or PT when multiple AEs are coded to the same SOC or PT.

AEs with missing intensity will be listed as such in the AE listings, however, will be summarized as severe in summary tables. If the relationship of an event is missing, the relationship for the event will be considered to have been related.

The TEAE summary tables will include numbers and percentages of subjects experiencing at least one TEAE by SOC and PT and will be tabulated. The following is a list of TEAE summary tables to be generated:

- Overview of TEAEs.
- TEAEs by SOC and PT
- Serious TEAEs by SOC and PT
- Drug-Related TEAEs by SOC and PT.

Also, non-treatment-emergent AEs will be summarized by SOC and PT. Data listings will be provided for all AEs including TEAEs, AEs leading to trial drug discontinuation, and SAEs.

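### Protocol 9.2.7 files health changes between an undefined baseline and dosing as medical history, while Section 10 and the SAP make untoward ones AEs, so nonserious pre-dose events can be missing from the non-treatment-emergent AE table

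*Protocol*

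**What the plan says.** Protocol 9.2.7 has three sentences. The first starts AE monitoring once consent has been signed. The second reads "Changes in subject health status from the baseline assessment until study drug administration should be captured in the subject's medical history". The third refers the reader to Section 10.0 for the full AE procedures.

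The rest of the protocol dates AEs from consent:

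- **10.1, definition:** "An AE is defined as any untoward medical occurrence in a clinical investigation subject who has signed informed consent to participate in a study".
- **10.1, what was already there at consent:** "A preexisting condition (present at the time of signing of informed consent) is considered a concurrent medical history condition and should NOT be recorded" (that is, it stays off the AE page). Any later worsening of it is an AE, with the timing given as "worsening or complication occurs after informed consent is signed".
- **10.2.8.1:** "Collection of AEs (AEs, SAEs, and abnormal LFTs) will commence when the subject signs the informed consent".
- **10.2.8.2:** all AEs go on the AE page of the eCRF. Nonserious events starting before first exposure are called AEs, and only their follow-up is waived.
- **10.2.8.3:** SAEs that begin before dosing are reported in the same way as on-treatment SAEs.

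The SAP follows Section 10. SAP 7.11.1 uses the same consent-based definition and adds: "Also, non-treatment-emergent AEs will be summarized by SOC and PT". SAP 7.5 states: "Medical history is defined as significant conditions or diseases that resolved at or prior to the time of informed consent". It defines concurrent conditions as those present or ongoing at consent. Both categories are listed only, without summary statistics.

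**The concern.** The same event has two destinations. Take a nonserious reaction to cannulation on Day 1, shortly before the infusion. Under 9.2.7 it is a change in health status before dosing and belongs in medical history. Under Section 10 it is an AE and belongs on the AE page. If it is filed as 9.2.7 directs, it fits neither SAP 7.5 category, because it was neither resolved by consent nor present at consent.

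The choice decides what can be reported. The AE page carries start and end times, severity, causality, seriousness and outcome (Protocol 10.2.8.2). Protocol 9.1.3 sets no such fields for medical history, and the listing described in SAP 7.5 includes none of them. An event sent there drops out of the non-treatment-emergent AE table and cannot appear in a summary of AEs related to study procedures. Safety and tolerability is the trial's only secondary objective, and with about 6 subjects a single event is visible in any table.

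**Working it through.** The plan has no figure of its own to reproduce here: SAP 6.0 says no formal sample size calculation was made. The check compares the texts and adds two small pieces of arithmetic.

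**Step 1. Trace one nonserious untoward event that starts after baseline and before dosing.**

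| Question | Following 9.2.7 | Following Section 10 and the SAP |
|---|---|---|
| Where is it recorded? | Medical history | AE page (10.1, 10.2.8.1, 10.2.8.2) |
| Does it fit the SAP category? | No: SAP 7.5 stops at consent | Yes: SAP 7.11.1 starts at consent |
| Severity, causality, outcome? | Not specified (9.1.3) | Required (10.2.8.2) |
| Planned output | Listing only (SAP 7.5) | Non-treatment-emergent AE table and AE listing (SAP 7.11.1) |

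**Step 2. Size in the affected table.** Inputs: 6 dosed subjects (Protocol 11.3, SAP 6.0) and, as an assumption, one subject with one such event.

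- Recorded on the AE page: 1/6 = 16.7%.
- Recorded only as medical history: 0/6 = 0%.
- The plan allows more than 6 dosed subjects. With 7, the contrast is 1/7 = 14.3% against 0%.

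**Step 3. Length of the window.** Section 9.2.7 does not define its baseline.

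- *Last observation before dosing (the general rule in SAP 7.1).* Vital signs and ECG are taken on Day 1 before the infusion, and laboratory tests and the physical examination within 24 hours before dosing (Schedule of Study Procedures). The window is hours, at most about a day.
- *Screening (the ECG rule in Protocol 9.2.5).* Screening falls on Day -28 to Day -2. By the day count in SAP 7.1.2, these are 28 and 2 days before Day 1, so the window is 2 to about 28 days.

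The cannulation example can fall inside the window under either reading, because Protocol 6.2.5 places vital signs and ECG before blood collection.

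**Step 4. Effect on the treatment-emergent AE endpoint.** SAP 7.11.1 counts events with onset on or after dosing. A new pre-dose event that does not worsen is not treatment-emergent by either route, so the percentage is the same. If it worsens after dosing, Protocol 10.1 has the worsening recorded as an AE in its own right, and SAP 7.11.1 admits a pretreatment AE or concurrent condition that increases in severity. What remains is that medical history holds no pre-dose severity for the comparison.

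**Step 5. SAEs.** Protocol 10.2.8.3 covers pre-dose SAEs expressly. The exposure is therefore nonserious events.

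**The case against.** The best defence is that 9.2.7 defers to Section 10.0 and never says that medical history replaces the AE page. Read as an additional entry, its middle sentence could stand beside the other two, and Section 10 is explicit about where AEs go. This reading is possible, but the text does not say that the entry is additional. Section 10 does not elaborate the 9.2.7 routing either; it gives a different one. Even dual entry would place post-consent events in a category that SAP 7.5 closes at consent. SAP 7.13 lists two departures from the protocol, and this is not one of them.

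Other parts of the defence stand and limit the point:

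- **The secondary endpoint.** A reader might infer that one misrouted subject moves the treatment-emergent AE percentage by 16.7 points. The documents do not support that (Step 4). The shift is in the non-treatment-emergent table, which is not an endpoint.
- **The window.** A reader might infer that the conflict covers most of AE collection: 28 of 28 + 14 = 42 days, or 67%. That borrows a baseline stated only for ECGs, which SAP 7.13 replaces for ECG summaries, and assumes consent and screening on Day -28.
- **SAEs.** A reader might infer that pre-dose SAEs could be lost. Protocol 10.2.8.3 rules this out.
- **Procedure-related AEs.** SAP 7.11.1 says AEs related to study drug and/or procedure are summarized separately, but the tables it then names include a drug-related one and no procedure-related one. The loss there applies to whatever summary is produced.
- **Not everything after consent is an AE.** Section 10.1 excludes, for example, intermittent events of pre-existing conditions. The fix must keep those exclusions.

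**Conclusion.** The conflict is real and should be corrected. As written, 9.2.7 sends nonserious events arising between its undefined baseline and dosing to medical history, while Section 10 and the SAP require untoward events after consent on the AE page. If the site follows 9.2.7, the non-treatment-emergent AE table is incomplete, as is any procedure-related summary. One affected subject among 6 is 16.7% against 0% in that table.

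This rests on three assumptions: at least one such event occurs, the site reads 9.2.7 as naming the only place of entry, and 6 subjects are dosed. The documents give no rate for pre-dose events, so the expected number lost cannot be estimated. The window is hours under the SAP's general baseline and at most about 28 days if baseline means screening.

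The consequence is confined to descriptive safety outputs. The primary endpoints are not touched, the treatment-emergent AE percentage is essentially unchanged, and pre-dose SAE reporting is secure.

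**What to change.** Replace the second sentence of Protocol 9.2.7 with:

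> Events that occur after signing of the ICF and before study drug administration and that meet the AE definition in Section 10.1 are recorded on the AE page of the eCRF as pretreatment AEs; only conditions resolved by or present at signing of the ICF are recorded as medical history or concurrent conditions.

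Align the eCRF completion guidance with it. The reference to Section 10.1 matters: wording that swept in every new event or worsening would override the exclusions there. The new sentence also removes the undefined baseline from the rule.

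The cost is one protocol sentence, the matching guidance and a few more AE pages. No SAP change is needed, because SAP 7.5 and 7.11.1 already work this way.
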